#### 3.4.6 PLANNED INTERIM ANALYSES

The Data Safety Monitoring Board (DSMB) will review safety data (including components of the primary endpoint, since these may impact safety) regularly to ensure that it is ethical to continue the study, based on the absence of unacceptable risks to the study cohort. There will be no formal interim analyses of the primary endpoint, however, the DSMB will review the primary effectiveness endpoint since ineffective treatment contributes to the overall benefit-risk profile of subject exposure to the Lava LES. The timing and frequency of safety monitoring will be described in the DSMB Charter.

#### 3.4.7 SUB-GROUP ANALYSES

Subgroup analyses will be performed for sex, target territory (gastrointestinal and non-gastrointestinal), and for etiology (traumatic and non-traumatic). The subgroup analyses will be descriptive in nature and will not be powered for hypothesis testing. Statistical hypothesis testing will be conducted to assess the similarity of the primary effectiveness endpoint across each sub-group using a Fisher's exact test and a significance level of 0.15.

Poolability of data across clinical study sites is justified based on clinical characteristics of the study design; all study sites use the same Protocol; sites are monitored for protocol compliance, and the data gathering instruments are identical. However, a statistical assessment of poolability will be performed by comparing the baseline characteristics across study sites. For categorical baseline variables such as sex, a generalized Fisher's exact test or equivalent test will be used and for quantitative variables,

parametric or non-parametric analysis of variance (general linear models or an equivalent procedure) will be used.

The above statistical analyses do not result in an impediment to pooling, but rather assess the balance of baseline covariates across study sites. If any baseline covariate is found to be statistically significant by this process, multivariate analyses will be done to determine if the imbalance affected study outcome. This is done by using both the variable found out of balance and study site as possible covariates.

The justification for pooling all the data to estimate a common effect across study sites requires the homogeneity of response across study sites. A Fisher-Freeman-Halton test analyzing the rates of success for the primary effectiveness endpoint, clinical success rate, will be employed to test whether investigational sites differ with respect to primary effectiveness. The test of inhomogeneity of response will be based on a two-sided test using a 0.15 level of significance. Study sites with fewer than 6 subjects will be excluded for the analysis of poolability.

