## 7.11 Subgroup and Other Analyses

Subgroup analyses for primary effectiveness endpoint, clinical success rate, will be performed for sex, target territory (gastrointestinal and non-gastrointestinal), and for etiology (traumatic and non-traumatic). The subgroup analyses will be descriptive in nature and will not be powered for hypothesis testing. Statistical hypothesis testing will be conducted to assess the similarity of the primary effectiveness endpoint across each sub-group using a Fisher's exact test and a significance level of 0.15.

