### 8.3 Target Lesions, Vessels, and Territories

The Target Lesion is specified by the Investigator at the index procedure, after diagnostic angiography but prior to embolization, and is defined as a hemorrhage site planned for embolization with the Lava LES. Up to 4 Target Lesions may be treated in a subject.

Target Vessels are arteries where the tip of the delivery catheter is located at the time Lava administration is planned.k More than one Target Vessel may supply a single Target Lesion. Each Target Lesion is linked to a Target Territory, where the Target Territory is defined as the vascular territory supplied by a Target Vessel, within a single organ, extremity, or tissue bed.l

Non-Target Embolization is defined when Lava is unintentionally administered to a vascular bed outside a Target Territory. Non-target territory is defined as the vascular territory outside of the planned Target Territory specified by the Investigator prior to embolization at that site. Inadvertent embolization of Lava to a Non-Target Territory is an element of the composite MAE endpoint.

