1. Technical Success, defined as absence of angiographic evidence of bleeding from the target lesion at the conclusion of the index procedure;
2. Successful delivery of Lava and intact retrieval of the microcatheter;
3. Assessment of each element of the primary safety endpoint (MAE) as an individual component within 30 days of the index procedure;
4. Symptomatic ischemia in the target territory that does not require intervention within 30 days of the index procedure;
5. All-cause mortality within 30 days of the index procedure;
6. Bleeding-related mortality (attributable to bleeding in a target territory) within 30 days of the index procedure;
7. Open surgical conversion for persistent or recurrent bleeding within 30 days of the index procedure;
8. Device-related serious adverse events within 30 days of the index procedure;
9. Procedure-related serious adverse events within 30 days of the index procedure;

 The effectiveness endpoint is lesion-based and not subject-based. Failure of the effectiveness endpoint is triggered by events that are referable to the specific lesion and not to other events referable to another lesion in the same subject. For example, if a subject has two lesions where the first is treated successfully but the other rebleeds and requires emergency surgery, effectiveness would have been achieved in the first lesion but not in the second.

 Core laboratory-determined assessment of bleeding is used for the primary and secondary endpoints. If core laboratory images are unavailable or uninterpretable, the site-reported determinations will be used.

10. Access site hematoma (>5cm in longest axis) within 30 days of the index procedure;
11. Access site false aneurysm within 30 days of the index procedure;
12. Units of red blood cells transfused after administration of Lava;
13. Duration of the index procedure, total and after administration of Lava;
14. Contrast administered the during index procedure;
15. Fluoroscopy time during the index procedure;
16. Length of stay in the intensive care unit after the index procedure;
17. Length of hospitalization, total and after the index procedure.

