### **Handling of Missing Data**

All attempts will be made to limit the amount of missing data. For all analyses of the primary endpoints, the number of observations available will be reported so the reader can assess the impact of missing data. In general, and for the primary endpoint analyses, missing data will not be imputed and analyses will be based on available data. For missing values on the primary safety endpoint, an adjustment to the denominator will be made based on the amount of evaluable data. For each visit (or reporting time point), the occurrence rate will be calculated as the number of subjects with certain endpoint occurrence term over the number of evaluable subjects. The evaluable subjects at each reporting time point include all subjects who are enrolled by the snapshot date and

- 1) had an endpoint occurrence within (on or before) the reporting cutoff days (30 days), or
- 2) had a follow-up at or after the lower limit of the reporting window (23 days), or
- 3) the withdrawal consent date/recorded lost-to-follow-up date at or after the lower limit of the reporting window.

Sensitivity analyses will be performed to assess the impact of missing data and potential correlation in the data for the primary endpoints. Three different sensitivity analysis are planned: (1) As described in the protocol, Target Lesions with unavailable effectiveness data will be assumed to have missing data at random and will be imputed by random selection with replacement of data from Target Lesions with complete data. (2) A tipping point analysis will be conducted in which lesions or subjects censored without an event prior to 30 days follow-up are sequentially imputed as failures at the time of censoring. (3) A generalized estimating equation (GEE) logistic regression model will be used to estimate clinical success taking into account potential correlation of multiple Target Lesions within a subject using an exchangeable working correlation structure. The analyses for all the secondary endpoints will not include imputation for missing data, and no formal statistical hypotheses will be tested.

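### The site and subgroup Fisher tests of lesion-level success ignore within-subject correlation and would reject above 0.15 if many subjects had several lesions, the site test most of all

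*SAP*

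**What the plan says.** SAP 3.4.7 (matching protocol 7.11 and 7.14) plans two kinds of comparison of Clinical Success.

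- Subgroups by sex, target territory and etiology: "Statistical hypothesis testing will be conducted to assess the similarity of the primary effectiveness endpoint across each sub-group". The method named is Fisher's exact test, at the 0.15 level. The same paragraph, like protocol 7.11, also says: "The subgroup analyses will be descriptive in nature and will not be powered for hypothesis testing".
- Sites: "A Fisher-Freeman-Halton test analyzing the rates of success for the primary effectiveness endpoint, clinical success rate", with the test "based on a two-sided test using a 0.15 level of significance". Sites with fewer than 6 subjects are left out.

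Section 3.4.7 does not name the unit of these tests. It follows from the endpoint, which SAP section 2 defines in a footnote: "The effectiveness endpoint is lesion-based and not subject-based". Protocol 8.3 adds: "Up to 4 Target Lesions may be treated in a subject".

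The SAP deals with clustering in one place only. Among the sensitivity analyses in SAP 3.4.1 (Handling of Missing Data) is a GEE logistic model for the clinical success estimate, "taking into account potential correlation of multiple Target Lesions within a subject using an exchangeable working correlation structure". It is not extended to the subgroup or site comparisons.

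**The concern.** A Fisher test on a table of lesions treats every lesion as an independent observation. Sex and site are the same for all lesions of one subject, and etiology usually is. If lesions in one subject tend to succeed or fail together, group success rates vary more than the test assumes, and its p-values come out too small.

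What is at stake is mainly the site comparison. SAP 3.4.7 says that pooling to a common effect requires homogeneous response across sites, and this is the test it names for that. A false signal in a single-arm pivotal study would have to be explained after the fact, and choosing a different unit of analysis at that stage would be less credible than fixing it now. For the subgroups the stake is smaller: a misleading flag in an analysis described as unpowered and descriptive.

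**Working it through.** **The plan's own figure.** Goal 72%, anticipated 84%, one-sided exact alpha 0.025 (SAP 3.2). At n = 101 the critical value is 82 successes, the exact alpha 0.0227 and the power 0.819. No smaller n reaches 80%, so 101 is reproduced. Attrition: 101 / 0.90 = 112.2, rounded up to 113. SAP Table 2 labels this 113 as Target Lesions and the text of 3.2 calls it 113 subjects, so the plan works with about one lesion per subject.

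**Simulation under a true null.** Inputs from the documents: 84% success, about 101 evaluable subjects, nominal level 0.15, at most 4 lesions per subject. Assumptions, because the documents give neither: the share of subjects with several lesions and the intra-subject correlation (ICC). Lesion outcomes are beta-binomial within subject, and all lesions of a subject fall in the same group. The subgroup test is a 2x2 Fisher test (50:50 and 30:70 splits, 5,000 runs). The site test is a Monte Carlo Fisher-Freeman-Halton test (10 sites of 10 or 6 sites of 16 subjects, 2,000 runs).

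Rejection rates at nominal 0.15, ICC 0.3 to 0.6:

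| Subjects with 1/2/3/4 lesions | Two-group Fisher | Site Fisher-Freeman-Halton |
|---|---|---|
| 100/0/0/0% | 0.11-0.12 | 0.13-0.15 |
| 90/10/0/0% | 0.12-0.13 | 0.17-0.22 |
| 80/12/5/3% | 0.16-0.19 | 0.24-0.40 |
| 50/25/15/10% | 0.19-0.26 | 0.32-0.64 |

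With ICC 0, every mix gives about 0.11 to 0.17, so the excess needs correlation as well as multiple lesions. A repeat at ICC 0.3 to 0.5 gave, for 20% and 50% multi-lesion subjects, 0.13-0.17 and 0.15-0.25 for two groups, and about 0.22-0.34 and 0.23-0.58 for 10 sites. These are the figures used in the conclusion.

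**Why sites suffer more.** The variance inflation is D = 1 + ICC x (E[m²]/E[m] - 1), with m lesions per subject. For the 80/12/5/3% mix, E[m] = 1.31 and E[m²] = 2.21, so D = 1.206 at ICC 0.3 and 1.412 at ICC 0.6. The 0.15 critical value of chi-square is 2.07 on 1 df and 13.29 on 9 df (10 sites). Dividing it by D:

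- 1 df: P(chi-square > 1.72) = 0.19 and P(chi-square > 1.47) = 0.23.
- 9 df: P(chi-square > 11.02) = 0.28 and P(chi-square > 9.41) = 0.40.

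The same inflation does more damage with more degrees of freedom. In the 2x2 case the conservatism of Fisher's test (0.11-0.12 with one lesion each) also absorbs part of it.

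**Candidate remedies.**

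- Permuting whole subjects, with a lesion-level statistic: 0.13-0.15 for two groups and 0.13-0.17 for 10 sites; 0.13-0.19 in the repeat. Within simulation error this is near 0.15.
- Fisher test on subjects, success meaning all lesions successful: with equal 84% lesion success but 10% versus 50% of subjects having two lesions, it rejects about 21-22% at ICC 0 and 18% at ICC 0.3. The lesion-level Fisher test gives 11% and 13%. At ICC 0.5 both are about 15%.
- GEE with site terms: with 10 sites of 10 one-lesion subjects, the chance that at least one site has 100% success is 1 - (1 - 0.84^10)^10 = 1 - (1 - 0.175)^10 = 0.85. That site's logistic term cannot then be estimated.

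**The case against.** The strongest reply is that the problem does not arise in the trial as planned. At about one lesion per subject the two-group tests run below 0.15 and the site test at about 0.15. With 10% of subjects having two lesions, the two-group tests still stay below 0.15 at ICC 0.3 to 0.6. The tests are also peripheral: a level of 0.15 is a lenient screen, no action is tied to crossing it, and an excess of flags does not favour the sponsor. Territory need not be a subject-level factor either, because protocol 8.3 links each lesion to its own territory.

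All of this stands and limits the point. It does not remove it. The protocol allows up to four lesions, the SAP itself anticipates correlation, and the site test is already at 0.17 to 0.22 when only 10% of subjects have two lesions.

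A reader might infer more than the documents support:

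- That all these tests are the evidence for pooling. SAP 3.4.7 discusses pooling over sites only, and rests it first on common protocol, monitoring and data collection. The sex, territory and etiology tests are not offered as pooling evidence.
- That the study conclusion is at risk. The success rule in SAP 3.1 and 3.4.2 uses only the two primary hypotheses.
- That inflation is to be expected. That depends on a lesion load the documents do not predict.

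**Conclusion.** The point holds conditionally and is minor. As written, the plan applies independence-based tests to lesion counts while acknowledging elsewhere that lesions in one subject may be correlated. With ICC 0.3 to 0.5, the nominal 0.15 becomes about 0.22-0.34 for the site test if 20% of subjects have several lesions, and 0.23-0.58 if 50% do. The two-group tests become about 0.13-0.17 and 0.15-0.25, and stay at or below 0.15 when few subjects have several lesions. These sizes rest on an assumed lesion mix, an assumed positive ICC and all of a subject's lesions lying in one group. The last is certain for sex and site, and only likely for etiology and territory. The consequence is a possible false signal of heterogeneity, and only the site signal bears on pooling. The tension between calling the subgroup analyses descriptive and testing them is a matter of wording, with no consequence elsewhere in the plan.

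**What to change.** In SAP 3.4.7, name the unit of analysis and make these changes:

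- Sites: keep the lesion-level success rate, but obtain the p-value by permuting whole subjects across sites, so that a subject's lesions move together.
- Subgroups: do the same for sex, and for etiology or territory where constant within subject. Alternatively, for these two-level factors, test a term in a GEE logistic model with the exchangeable structure specified in SAP 3.4.1.
- State that the 0.15 subgroup results are descriptive flags.

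Two apparent shortcuts should be avoided. The all-lesions-successful Fisher test changes the endpoint and is invalid when lesion counts differ between groups. GEE site terms will often not be estimable.

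The cost is a few lines of SAP text, a little extra programming (the GEE is specified, but without subgroup or site terms) and slightly less power to flag heterogeneity. The permutation check above used the same lesion mix in every group; unequal mixes were not simulated. No new data are needed and the primary analysis is unchanged.

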#### 3.4.8 TABULATION OF INDIVIDUAL PARTICIPANT DATA

Individual participant data will be listed by measure and time point.

#### 3.4.9 EXPLORATORY ANALYSES

There are no exploratory analyses planned for this study.

### 4 DATA HANDLING AND QUALITY ASSURANCE

#### 4.1 DATA MANAGEMENT

Refer to the Data Management Plan (DMP).

#### 4.2 QUALITY ASSURANCE

Refer to the Quality Assurance SOP for the quality assurance plan.

#### 4.3 ACCESS TO RAW DATA AND ANALYSIS RESULTS

Refer the DMP for the database information. For the analysis results, access is limited to the programmers and the statistician until all patients have reached all the powered endpoints, the database is cleaned and ready for analysis and the primary endpoint analysis is complete.

## 5 ABBREVIATIONS

AE	Adverse Event
CC	Complete Cases
CMP	Clinical Monitoring Plan
DMP	Data Management Plan
DSMB	Data Safety Monitoring Board
eCRF	Electronic Case Report Forms
IDE	Investigational Device Exemption
ITT	Intention-To-Treat
MedDRA	Medical Dictionary for Regulatory Activities
SAP	Statistical Analysis Plan
SOC	System Organ Class
SOP	Standard Operating Procedure
US	United States

## 6 REFERENCES

There are no references for this study.

## 7 APPENDICES

There are no appendices for this study.
